Low vision rehabilitation (LVR) can improve functional ability for individuals with low vision (LV), but effectiveness depends on and increases when rehabilitation techniques are applied over repeated training sessions to reinforce patient motivation, compliance, and skills in the correct use of magnification devices. The skills taught by LVR providers in-office may not translate when patients use their magnification devices at home, either because the lighting and ergonomics are not ideal, or they do not retain the specific instructions for using the device. Successful use of these devices requires the correct working distance, proper viewing angle, application to appropriate types of near tasks, use

with the better eye, eccentric viewing techniques and/or spectacle correction in some cases. Magnification devices are abandoned by LV patients when they are perceived as ineffective for the task, which is likely preventable by attending follow-up visits for additional LVR to maximize visual function with the device. The most common outpatient-based approach for delivering LVR training in-office has significant limitations since patients have difficulty returning due to geographic and/or transportation barriers. Roughly 70% are no longer able to drive. Access to LVR care in the developed world is estimated to be as low as 10 to 20%. As there is currently a paucity of LVR providers, access is particularly limited in rural areas of the United States. Physical disability and chronic illness prevalent in this population can prevent care utilization, as LVR may seem implausible due to patients' frailty or busy appointment schedules for comorbidities. Vision loss can lead to reduced quality of life, increased depression, anxiety, and/or emotional distress; these issues may persist after an initial LVR encounter if follow-up training is not given to best utilize patients' remaining vision by learning to correctly use magnification devices.

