Our primary outcome measure, the Activity Inventory questionnaire, and the secondary outcome measure, the Sustained Silent Reading test by Ramulu et al., will be administered by phone by a UCLA research assistant at baseline (time of study entry), one month following receipt of the new magnification device, and four months after receipt of the magnification device (at time of study completion). The SF-36 general health questionnaire, Telephone Interview for Cognitive Status (TICS), Geriatric Depression Scale, and Hospital Anxiety Depression Scale questionnaires will be administered by phone by a UCLA research assistant at baseline (time of study entry), and four months after receipt of the magnification device (at time of study completion). The MNread test will be administered by the OD/OT provider at each in-office visit and/or during telerehabilitation sessions. Within 24 hours of each telerehabilitation session or in-office rehabilitation session, the UCLA research assistant will administer a satisfaction survey by phone. To characterize participants' baseline level of visual impairment, we will gather information from a medical record review from each our sites, in which we will record the results from validated visual acuity and contrast sensitivity tests at the initial in-office visit. These vision tests are used as part of standard of care.

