The PI will be responsible for training the research assistants in basic interview skills and instructions for administering the survey instruments, as well as internal quality assurance measures. To help assure the quality and consistency of responses from participants for our primary and secondary outcomes, the PI will instruct the research assistants involved in data collection to adopt a neutral demeanor and interviewing style when administering the questionnaire (i.e., avoid directing, guessing responses; suspend judgment, but not standoff-ish). The PI will periodically observe about 10% of the survey administrations throughout the study to confirm they are being conducted consistently and according to instructions. The research assistants will be trained to respond to possible depression or suicidality by connecting the at-risk participants to someone by phone by either calling 911 or someone at the National Suicide Prevention Lifeline. If a subject indicates suicidal ideation and indicates that they have means and intent to accomplish this, the study team will keep the subject on the telephone while asking another study team member in the participant's local area to telephone 911 for immediate intervention. If the study team encounters a subject who expresses suicidal ideation or suicidal intent, they will keep the subject on the phone call until they are able to transfer the subject to speak to a specialist at the National Suicide Prevention Lifeline. In the case of severe depression or anxiety, we will refer them to see their internist or general physician so they can find appropriate care locally. The cut-off scores that will trigger referral are ≤ 38 for the SF-36 mental component summary, ≥ 12 for the Geriatric Depression Scale, and ≥ 11 for the Hospital Anxiety Depression Scale (HADS-D). These three questionnaires will be scored while the subject is still on the telephone and study personnel will let the subject know that they will be making the referral for

follow-up evaluation with their primary care provider.

Procedures at each study site

- Marshall B Ketchum University, Southern California College of Optometry: subject identification, recruitment, conduct of vision rehabilitation training sessions in-office or via telerehabilitation, and data collection procedures from in-office visits

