Multiple regression analyses will assess if effect sizes for the telerehabilitation and in-office LVR control group (i.e., changes in the outcomes: Activity Inventory score, reading speed) are related to the number of telerehabilitation sessions, patient demographics, visual acuity, contrast sensitivity, diagnosis, or scores on the SF36, Telephone Interview for Cognitive Status (TICS), Geriatric Depression Scale, or Hospital Anxiety Depression Scale questionnaires. We will apply advanced statistical methods (e.g., multilevel models) for missing data. We will perform a Rasch analysis of our Activity Inventory data in comparison to a very large database of LV patients (several thousand) who have completed the Activity Inventory. Goals and activities have their item measures, and the fit properties of the Activity Inventory from the database of previous responses can be used to convert raw scores into person measures. In the event of non-normally distributed data, we will use a binary outcome (proportion of subjects with improvement greater than 0.14 logits) to compare changes between telerehabilitation and in-office LVR for the Activity Inventory domains using chi-square tests and logistic regressions.

Sample Size calculation: We plan to enroll and compare findings for two equal sized groups based on visual acuity (VA); i.e., those better or worse than 20/63. A sample size calculation for matched pairs t-test revealed that 18 subjects in each of the 2 groups would detect a within-subject mean improvement of 0.14 logits on the Activity Inventory (primary outcome) following telerehabilitation (equivalent to 1-line or 0.1 logMAR VA), when considering a standard deviation of 0.17 logits for the differences, power of 0.80 and 0.05 type I error probability. We will aim to enroll a total of ~40 subjects randomized to telerehabilitation (given our 2:1 randomization plan), and aim to have a total of ~20 active controls randomized to receive in-office LVR. We will determine the effect sizes for basic LVR (one session in-office as part of standard of care), telerehabilitation and additional in-office LVR for changes in the Activity Inventory and reading outcomes.

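### Referral is promised for severe anxiety, but if HADS-D means the depression part of the scale, none of the three listed cut-offs is specific to anxiety

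*Combined protocol and SAP*

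**What the plan says.** The rule is in the combined protocol and SAP, under Outcome measures, in the paragraph on training the research assistants. The commitment reads: "In the case of severe depression or anxiety, we will refer them to see their internist or general physician". The triggers follow at once: "The cut-off scores that will trigger referral are ≤ 38 for the SF-36 mental component summary", then "≥ 12 for the Geriatric Depression Scale, and ≥ 11 for the Hospital Anxiety Depression Scale (HADS-D" (the closing bracket follows in the text).

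The rule is applied during the call: "These three questionnaires will be scored while the subject is still on the telephone", and the participant is told then that a referral will be made.

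Two other places name the scale. Earlier under Outcome measures, the schedule says "Geriatric Depression Scale, and Hospital Anxiety Depression Scale questionnaires will be administered by phone by a UCLA research assistant at baseline" and again at four months. Under Statistics and Data Analysis, the regressions use "scores on the SF36, Telephone Interview for Cognitive Status (TICS), Geriatric Depression Scale, or Hospital Anxiety Depression Scale questionnaires" as possible predictors. Neither place uses the suffix or says whether a part score or a total is meant.

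Background and Significance treats anxiety as foreseeable in these patients: "Vision loss can lead to reduced quality of life, increased depression, anxiety, and/or emotional distress".

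**The concern.** The commitment names two conditions, and the list of cut-offs is what puts it into practice. One condition, depression, has a scale of its own in that list. The other, anxiety, has a specific score only if the third trigger is something other than what its suffix suggests.

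What is at stake is a participant-safety promise. A rule followed exactly as written could leave a severely anxious participant without the referral that the preceding sentence offers. Because scoring happens while the participant is on the phone, the score to use and the value that counts need to be settled beforehand. Nothing about the estimated effect of telerehabilitation depends on this.

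**Working it through.** The check is mainly a comparison of texts. The plan gives no figure to reproduce.

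**Step 1. Match each trigger to the promised conditions.**

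| Trigger | What it measures | Specific to anxiety? |
|---|---|---|
| SF-36 mental component summary, 38 or less | General mental health | No |
| Geriatric Depression Scale, 12 or more | Depression, by its name | No |
| HADS-D, 11 or more | Undefined; the suffix suggests the depression part | No, if the suffix means depression |

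On the reading that the suffix suggests, 0 of 3 triggers are specific to anxiety.

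**Step 2. Look for a definition elsewhere.** HADS-D appears once. The administration schedule and the regression plan name the questionnaire as a whole. No separate anxiety score or anxiety cut-off appears in the text available. The wording about three questionnaires being scored on the call presents the trigger list as complete.

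**Step 3. Follow each reading through.** Assume that the HADS total is an anxiety part A plus a depression part D, neither negative. The documents do not describe the scoring, so this is an assumption.

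- Depression part meant: the trigger fires if D ≥ 11. A participant with a high A, D below 11, a mental component summary above 38 and a Geriatric Depression Scale score below 12 meets no trigger.
- Total meant: the trigger fires if A + D ≥ 11. Anxiety items then count, but the suffix is wrong and the text does not say that the total is the score to compare with 11.

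Two examples show that the choice changes the action. With A = 11 and D = 0, the depression reading does not fire (0 < 11) and the total reading does (11 + 0 = 11). With A = 6 and D = 5, the depression reading does not fire (5 < 11) and the total reading does (6 + 5 = 11). These values were picked to separate the readings and say nothing about how often such scores occur.

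**Step 4. How often the rule is used.** Specific Aims plans 60 participants, and the questionnaires are given at two time points, so the rule is applied up to 2 × 60 = 120 times. That counts applications, not missed referrals. The number of missed referrals cannot be worked out from the documents.

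**Step 5. Effect of adding an anxiety cut-off.** Take 11 for each part as an illustration, so that the rule fires if D ≥ 11 or A ≥ 11. It refers everyone whom the depression reading refers. Since A ≥ 11 or D ≥ 11 implies A + D ≥ 11, it fires for no one for whom the total reading would not.

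**The case against.** The strongest reply is that the central reading is an inference. The suffix is undefined, it stands next to the full name of the scale, and the documents never say that the scale has separately scored parts. This stands, and it is why the point is conditional.

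A second reply is that the plan promises referral for anxiety, not an anxiety-specific score, and that the mental component summary is one of the tools chosen to deliver it. This also stands in part. A reader might infer that anxiety goes unscreened, or that any anxious participant caught by the general summary is caught by accident. The documents support neither: the summary is listed directly after the commitment and may well pick up some of these participants. What remains is that a participant can score high on anxiety and still meet none of the three cut-offs.

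A reader might also take the training sentence, "The research assistants will be trained to respond to possible depression or suicidality", as evidence that anxiety was left out of the assistants' task. It is not. That sentence introduces the crisis response by emergency call or suicide lifeline. Primary-care referral comes later and does name anxiety.

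Nor do the documents show that assistants would be unable to score the scale. The principal investigator trains them in the instruments and observes about 10% of administrations, so training may settle the label. Referral on judgement is not excluded either. But neither supplies a written anxiety threshold, which the plan does supply for depression.

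Finally, the trial is described as minimal risk, and suicidality has its own explicit pathway. That bears on how serious the point is, and it is fair.

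**Conclusion.** The point holds in a limited form. If HADS-D denotes the depression part of the scale, the plan promises referral for severe anxiety without any anxiety-specific trigger, and a participant with a high HADS anxiety score who meets none of the three cut-offs is not referred by the stated rule. If the total was meant, the defect is instead a wrong label on an operative threshold. The documents do not settle which.

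The number of participants affected is unknown, and it would go beyond the documents to infer that referrals will be missed in any particular number. The conclusion rests on reading the suffix as depression and on the scale having a separable anxiety score. The treatment comparison, sample size and error rates are untouched. This is a minor safety improvement worth making, not a flaw in the design.

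**What to change.** In the referral paragraph under Outcome measures, state that the cut-off of 11 applies to the HADS depression score, and add a cut-off on the HADS anxiety score as a further trigger. The sponsor should set the value. Using 11 again is the simplest option, but it is an assumption and does not come from the documents. If the total score was intended, remove the suffix and say that the total is compared with 11.

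The cost is one clarified label and one added cut-off. The questionnaire is already given and scored on the same call, so no extra instrument, call or staff is needed. The downside is some additional primary-care referrals compared with the depression-only reading, in a number that the documents do not allow one to estimate. With 11 on each part, and the total taken as the sum of the two, HADS-triggered referrals would not exceed those under the total-score reading.

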Per study visit/session to receive telerehabilitation or training in-office = approx. one hour

Per study telerehabilitation session to complete follow-up survey = approx. 15-30 minutes

Per study session to complete questionnaire outcome measures by phone = approx. 2-3 hours

Total anticipated time commitment per subject = approx. 8-15 hours over 4 months

Statistics and Data Analysis: Describe the proposed statistical procedures or descriptive analyses for the study. If applicable, indicate how the sample size was determined.

Data analyses: Data management will be an ongoing task for the PI.

Descriptive statistics will be used to summarize the study data and findings. We will determine the effect sizes for basic LVR (one session in-office as part of standard of care), additional in-office LVR (active control), and telerehabilitation for changes in the Activity Inventory and reading outcomes by comparing the scores at each follow-up to baseline (pre-LVR). For the Activity Inventory questionnaire, we anticipate that the reading domain may have the largest magnitude of change since magnification devices are most often used for reading tasks, which is the chief complaint of most LV

patients. For the MNread test, we will primarily focus our analyses on reading acuity and maximum reading speed. Separate analyses (sub-groups) for all outcomes will be used to compare outcomes for participants with hand-held or stand-based magnifiers (optical or electronic) versus spectacle-based high add power magnification (hands-free).

Multiple regression analyses will assess if effect sizes for the telerehabilitation and in-office LVR control group (i.e., changes in the outcomes: Activity Inventory score, reading speed) are related to the number of telerehabilitation sessions, patient demographics, visual acuity, contrast sensitivity, diagnosis, or scores on the SF36, Telephone Interview for Cognitive Status (TICS), Geriatric Depression Scale, or Hospital Anxiety Depression Scale questionnaires. We will apply advanced statistical methods (e.g., multilevel models) for missing data. We will perform a Rasch analysis of our Activity Inventory data in comparison to a very large database of LV patients (several thousand) who have completed the Activity Inventory. Goals and activities have their item measures, and the fit properties of the Activity Inventory from the database of previous responses can be used to convert raw scores into person measures. In the event of non-normally distributed data, we will use a binary outcome (proportion of subjects with improvement greater than 0.14 logits) to compare changes between telerehabilitation and in-office LVR for the Activity Inventory domains using chi-square tests and logistic regressions.

Sample Size calculation: We plan to enroll and compare findings for two equal sized groups based on visual acuity (VA); i.e., those better or worse than 20/63. A sample size calculation for matched pairs t-test revealed that 18 subjects in each of the 2 groups would detect a within-subject mean improvement of 0.14 logits on the Activity Inventory (primary outcome) following telerehabilitation (equivalent to 1-line or 0.1 logMAR VA), when considering a standard deviation of 0.17 logits for the differences, power of 0.80 and 0.05 type I error probability. We will aim to enroll a total of ~40 subjects randomized to telerehabilitation (given our 2:1 randomization plan), and aim to have a total of ~20 active controls randomized to receive in-office LVR. We will determine the effect sizes for basic LVR (one session in-office as part of standard of care), telerehabilitation and additional in-office LVR for changes in the Activity Inventory and reading outcomes.

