To assess the potential for telerehabilitation to enhance visual function by providing remotely-delivered LVR training to use magnification devices (i.e., hand-held or stand optical magnifiers, electronic magnifiers). Following basic LVR (i.e., one in-office training session) for new magnification device(s), we aim to determine if there is additional gain in visual functioning by randomizing subjects (2:1) to telerehabilitation or additional in-office LVR (active control). This will help provide estimates of effect size to plan a future larger-scale randomized controlled trial. We will compare visual function changes with the Activity Inventory questionnaire and validated reading tests in 60 LV patients with central vision loss due to any ocular disease recruited from 10 centers. Participants will be assessed before and after two consecutive periods: (1) no further training will be provided for one month after a single LVR training session (i.e., basic LVR), followed by (2) up to three LVR sessions over a three month period either via telerehabilitation (n=40) in the participants' homes with study loaner equipment (iPad/smartphone, stand, reading cards) via remote control assistance, or in-office LVR (active control; n=20). Multiple sessions will be conducted if the LVR provider deems the participant is not completely proficient with their magnification device. We will determine which patient characteristics and/or magnification devices are most likely to benefit from telerehabilitation, to be targeted in a future, larger-scale, phase III trial.

The primary goal of this proposal is to refine the methods and procedures for implementing these innovative technologies for LVR, in order to develop future protocols for randomized controlled trials. In the future, we envision that telerehabilitation could improve efficiency and patient outcomes by changing the method by which follow-up LVR services are provided. This is a high priority given the increasing prevalence of LV, paucity of LVR providers, and barriers related to transportation and geography.

Background and Significance: Provide a summary of the background for this study and explain how it will contribute to existing knowledge.

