Survey responses were collected over 1-2 months during November 2017 to January 2018 from LV patients seen for LVR and who received a magnification device at two of our proposed study centers. UNMC collected the following 62 survey responses over 2 months: mean age was 81 years (range 56-98), 42% were male, and 76% had age-related macular degeneration. About half of UNMC LV patients (52%) indicated that they were somewhat or very willing to have both a beacon sensor on their magnifier and a telerehabilitation session from their home if a community volunteer set up the loaner equipment for the session at no cost, with roughly a fifth (n=12; 19.4%) were very willing to do both. No experience with or no interest in computers was the primary reason for lack of willingness to try telerehabilitation in half of UNMC patients who declined telerehabilitation even after we offered the community volunteers. There were no significant differences in responses according to satellite location (site) or ocular diagnosis (all $P>0.05$), but older patients ($P=0.03$) and men ($P=0.009$) at UNMC were significantly less likely to be very willing to try both interventions. The site PI at SCCO had an unusually reduced LV clinic schedule and only five surveys were administered to eligible patients at SCCO over a month; however, 4 of 5 were somewhat or very willing to have both telerehabilitation and a beacon sensor, and one was very willing to do both, providing support for the feasibility to recruit at least one patient per month as per the plan for his site.

Research Design and Methods: Describe in detail the design and methodology of the study.

Research Plan and Methods:

We propose a minimal risk, phase 1/2 randomized controlled trial of telerehabilitation vs. in-office LVR (i.e., standard of care). The clinical trial in this proposal will include a run-in period to assess basic LVR (i.e., a single session in-office, which is part of standard of care, that all participants will receive) followed by randomization to one of two intervention groups (multiple telerehabilitation sessions with LVR provider vs. LVR in-office with the LVR provider). Our active control intervention for LVR in-office

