technique (i.e., working distance, lighting) and reading fluency (i.e., speed, accuracy, print size) with their magnifier device. In addition, they will ask the participant to read or view their own materials of interest, while providing LVR training. If relevant, the providers will ask participants to demonstrate how to change the battery in the magnification device, or to walk around their home with the smartphone to show the illumination levels in places where they use their magnifier. We will continually assess the telerehabilitation survey responses we will collect from both the LVR providers from our clinical centers and participants, in order to resolve any reoccurring problems related to Internet connectivity, videoconference portal, hardware devices, or audio/visual quality.

Hypothesized Outcomes, Sample Size Calculation and Data Analyses

Our outcomes that are questionnaires or reading tests will be assessed by phone by a different UCLA research assistant at each evaluation. It is not possible to mask the participants or LVR providers. The outcomes assessors will be identically trained by the PI. We successfully administered reading tests by phone in a previous study by providing the materials in a sealed envelope that the subject opens only at the test exam time. Our two interventions (telerehabilitation versus additional in-office LVR) may have similar effects since the same LVR principles will be applied at the same planned schedule of sessions; however, it is possible that telerehabilitation may be more beneficial if compliance with scheduled sessions is better than in-office LVR and/or if home-based training is advantageous in the patient's own environment with relevant tasks of interest; on the other hand, there may be aspects of LVR training that work better in-person and in-office. In-office LVR or at-home LVR with a therapist in-person are currently considered standard of care. All participants will receive standard of care since they will all receive one in-office LVR training session prior to randomization.

Outcome measures

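### Effect sizes for the randomised training are taken from the pre-LVR baseline, so they include first-month change, and the only between-arm method named is a responder fallback

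*Combined protocol and SAP*

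**What the plan says.** The Specific Aims set the question for the randomised phase: "we aim to determine if there is additional gain in visual functioning by randomizing subjects (2:1) to telerehabilitation or additional in-office LVR (active control". They describe two stages, a month without further training after one basic session and then three months of randomised training, and state that "Participants will be assessed before and after two consecutive periods". Research Plan and Methods confirms that the trial "will include a run-in period to assess basic LVR" before randomisation. Outcome measures schedules the Activity Inventory (primary) and the silent reading test (secondary) at study entry, month 1 and month 4.

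On analysis, the Statistics and Data Analysis section offers the following.

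- A general statement: "Descriptive statistics will be used to summarize the study data and findings".
- Effect sizes for basic LVR, additional in-office LVR and telerehabilitation, all obtained "for changes in the Activity Inventory and reading outcomes by comparing the scores at each follow-up to baseline (pre-LVR".
- Multiple regressions asking whether changes in the two groups "are related to the number of telerehabilitation sessions, patient demographics, visual acuity, contrast sensitivity, diagnosis, or scores on the SF36", with further questionnaires. Randomised arm is not among the listed terms.
- Multilevel models, mentioned as a way to handle missing data.
- For non-normal data only: "we will use a binary outcome (proportion of subjects with improvement greater than 0.14 logits) to compare changes between telerehabilitation and in-office LVR", by chi-square tests and logistic regression on the Activity Inventory domains.

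The section on hypothesised outcomes says "Our two interventions (telerehabilitation versus additional in-office LVR) may have similar effects" and then gives reasons why either arm might do better. It names no method for finding out.

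**The concern.** There are two linked gaps.

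First, the reference visit does not match the aim. The added value of the randomised training is the change from month 1 to month 4. A month-4 score set against the pre-LVR baseline measures that change plus everything that happened in the first month.

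Second, the trial randomises, yet if the data are normal no method is named for the randomised comparison. If they are non-normal, the method named discards information and leaves its starting visit open.

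The study exists to supply effect sizes for a later trial of telerehabilitation against in-office LVR, possibly an equivalence trial (Specific Aims; Background and Significance). That trial needs the between-arm difference with its interval and the SD of month-1-to-4 change. The plan asks for none of these. If the first-month change is positive, a planner who takes the within-arm effect as printed would credit the extra training with benefit that basic LVR produced.

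**Working it through.** **Inputs from the documents.** About 40 telerehabilitation and 20 in-office participants; SD of differences 0.17 logits; target within-subject improvement 0.14 logits; power 0.80; type I error 0.05 (Sample Size calculation). The interval to which the 0.17 applies is not stated. The documents give no basic-LVR gain and no distribution, so those are assumptions below. SD 0.17 is assumed in both arms unless varied.

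**The plan's own figure.** The sample size rests on a matched-pairs t-test with standardised effect 0.14/0.17 = 0.824. A two-sided noncentral-t calculation gives 14 per visual-acuity group at 80% power. The stated 18 gives 90.8%. This mismatch is a separate matter. What counts here is that the calculation is within-subject and sizes no between-arm comparison.

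**What the pre-LVR reference measures.** With Y0, Y1 and Y4 the scores at baseline, month 1 and month 4:

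Y4 − Y0 = (Y1 − Y0) + (Y4 − Y1)

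The first bracket is basic LVR plus any drift; the second is the randomised training phase. With complete data the mean of the second bracket follows by subtracting two planned means. Its SD does not, because Var(Y4 − Y1) = Var(Y4 − Y0) + Var(Y1 − Y0) − 2 Cov(Y4 − Y0, Y1 − Y0), and the covariance is not a planned summary.

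**Size of the within-arm excess**, as assumed basic gain / 0.17:

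- 0.05 / 0.17 = 0.29 SD
- 0.10 / 0.17 = 0.59 SD
- 0.14 / 0.17 = 0.82 SD

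Suppose the randomised training adds nothing. A paired t-test on pre-LVR-to-month-4 change with n = 40 would still be significant in 72% of trials if the basic gain is 0.07, and in 99.9% if it is 0.14.

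**Responder share with no gain after month 1.** The share above 0.14 logits is 0.17–0.21 if counted from month 1. Counted from pre-LVR it is 0.28–0.39 for a basic gain of 0.07 and 0.42–0.58 for 0.14. The ranges cover a normal shape and skewness 1.32 in either direction.

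**Precision of the missing contrast.** 95% half-width = t(0.975, 58) × SD × √(1/40 + 1/20) = 2.002 × SD × 0.2739.

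| SD | Half-width (logits) | t-test power for a 0.14 difference |
|---|---|---|
| 0.17 | 0.093 | 0.84 |
| 0.20 | 0.110 | 0.71 |
| 0.25 | 0.137 | 0.52 |

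Adjusting for month 1 multiplies the half-width by √((1 + r)/2) if the month-1 and month-4 SDs are equal. For an assumed correlation r of 0.5, 0.7 or 0.9, 0.093 falls to 0.081, 0.086 or 0.091. For comparison, the paired half-width within the telerehabilitation arm (n = 40, SD 0.17) is 0.054.

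**Power of the fallback.** Simulation with 10,000 runs per setting, 40 v 20, true difference 0.14, SD 0.17, cut at 0.14. Shapes are rescaled lognormals and their mirror images. The chi-square test is uncorrected; the rank test is Mann-Whitney.

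| Skewness | Chi-square power at control mean change 0 / 0.07 / 0.14 | Rank test |
|---|---|---|
| 0.78 right | 0.546 / 0.696 / 0.763 | 0.84–0.85 |
| 0.78 left | 0.765 / 0.693 / 0.569 | 0.86–0.87 |
| 1.32 right | 0.511 / 0.711 / 0.856 | 0.89 |
| 1.32 left | 0.847 / 0.705 / 0.546 | 0.91–0.92 |
| 2.26 right | 0.464 / 0.751 / 0.954 | 0.94–0.95 |
| 2.26 left | 0.955 / 0.760 / 0.513 | 0.975 |
| 3.69 right | 0.429 / 0.836 / 0.999 | 0.98 |
| 3.69 left | 0.999 / 0.835 / 0.478 | 0.996 |

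Chi-square is lower in all 12 settings at skewness 0.78 and 1.32. Above that it draws level or edges ahead only where the control mean happens to suit the cut. Unadjusted logistic regression is within 0.05 of chi-square throughout.

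**The case against.** The best counter-argument is that this is an early-phase, largely descriptive study whose stated primary goal is to refine methods, and that the scores needed for the right analysis are already collected. The protocol says it will compare changes in visual function, lists separate effect sizes for each training component, and reserves the binary comparison for non-normal data. All of this suggests that a period-specific analysis and an ordinary comparison of means were intended. The basic-LVR gain also cancels in expectation between arms. These points are fair. They mean that nothing is lost in data collection, but an implied analysis is not a specified one, and the written rule gives a different quantity.

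The size of the excess is also open to challenge, and these qualifications stand.

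- **Sign.** The first-month change could be nil or negative, in which case nothing is overstated.
- **SD.** If the pre-LVR-to-month-4 SD were 0.25, while month-1-to-4 change had mean 0.14 and SD 0.17, the standardised excess would be (0.14 + gain)/0.25 − 0.14/0.17. That is −0.06, 0.14 and 0.30 for gains of 0.05, 0.10 and 0.14.
- **Baseline timing.** Outcome measures places baseline at study entry, and eligible patients have newly received their devices, so part of the basic-LVR gain may already be in the baseline. The analysis section does say pre-LVR, however, and any baseline-to-month-4 change still contains first-month change.
- **Fallback power.** The plan's 0.14 logits is a within-subject improvement and no between-arm power is claimed. The simulations test a between-arm difference of that size only as an illustration, and a covariate-adjusted logistic model was not simulated.

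**Conclusion.** The concern holds and should be fixed. Followed literally, the plan reports within-arm effects that combine two periods the design was built to separate, and it leaves the randomised contrast without a named continuous estimate or interval. Both conclusions rest on the text alone.

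The magnitudes are illustrative. The 0.29–0.82 SD excess needs a positive first-month gain of the assumed size, a baseline that precedes basic LVR, and one SD of 0.17 for both intervals. The half-widths need a common SD and full enrolment of 40 and 20. The loss from dichotomising depends on the shape of the data and on where the arms sit relative to 0.14 logits; at moderate skewness it appeared in every setting tried. The trial need not be powered between arms, but it does need to say what it will estimate.

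**What to change.** 1. Name the main estimate: telerehabilitation minus in-office LVR in month-4 Activity Inventory person measure, analysed as randomised and adjusted for the month-1 score (ANCOVA or an equivalent mixed model), with a 95% CI.
2. State the expected precision: about ±0.09 logits at 40 v 20 if the SD is 0.17 in both arms, and about ±0.11 to ±0.14 if it is 0.20 to 0.25, before any gain from adjustment.
3. If the data are non-normal, keep the same contrast, with a rank or permutation test and a bootstrap CI. Report the proportion improving by more than 0.14 logits as supportive, and state the visit from which improvement is counted.
4. Report within-arm change, with SD and CI, separately for baseline to month 1 (basic LVR) and month 1 to month 4 (randomised training).

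The cost is revised analysis wording and one model, with no extra visits, data or participants. The price is a less flattering headline: an interval of about ±0.093 logits between arms, against ±0.054 for change within the telerehabilitation arm.
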